7 STUDY TIMELINES

- During the 3+3 component, accrual will be suspended until the three patients in each cohort have completed the DLT window (6 weeks after the last patient has begun therapy).
- Patients will be enrolled and treated on study for as long as they are deriving clinical benefit. Treatment on study has no specified end time.
 - Median progression free survival for patients with MDS receiving hypomethylating agents on clinical trials is between 18 and 24 months.
 - This study is therefore likely to enroll all 18 patients within 2 years and all patients are likely to have completed the study within 7 years of study opening.
- An interim analysis of correlative studies will be performed after every 3 patients have been enrolled and treated on the study for at least 5 months or come off treatment, whichever comes first.
- Given the long half-life for nivolumab and the known risk of late presenting adverse events, patients enrolled and treated on study will be followed for AEs for 180 days after the last dose of nivolumab.
- Patients will stay on study for 5 years after the last patient has been enrolled or until disease progression, whichever occurs first.

8 STUDY ENDPOINTS

8.1 Primary Endpoint

- To determine the safety of NY-ESO-1 vaccination (Anti-DEC-205-NY-ESO-1 fusion protein (CDX-1401)/poly ICLC) given in combination with decitabine and nivolumab.
 - This is a modified 3+3 design with a 12 patient expansion cohort at the maximum tolerated dose (MTD) or the maximum administered dose (MAD). We expect 18 patients to be enrolled (all at Dose Level +1(DL1)), given experience with these treatments in other studies. In DL1, decitabine will be given at 20 mg/m²/day,

PROTOCOL TITLE: I 49217 - Phase 1 CDX-1401/ Poly-ICLC +Decitabine +Nivolumab in
Patients with MDS or Low Blast Count AML

intravenously, over 1 hour on days 1-5 followed by 23 days without decitabine. If required, dose de-escalation of decitabine to 15 mg/m² is provided for during the safety portion of the study.

- The DLT window will begin on day -14 of cycle 1 and end on day 1 of cycle 2. The first cohort will enroll 3 patients and the DLT window for these 3 patients will end when the last patient in this group has reached cycle 2 day 1 of therapy. A second group of 3 patients will then be enrolled and treated.

All AEs and DLTs will be collected and used for descriptive characteristics for the purposes of the study.

8.2 Secondary Endpoint(s)

- To evaluate the induction of NY-ESO-1 specific cellular and humoral immunity by determination of NY-ESO-1 specific antibody, and NY-ESO-1 specific T-cell responses following standard treatment with decitabine in conjunction with immune sensitization with CDX-1401/poly-ICLC and nivolumab.
 - To evaluate the Immune cell profile in the peripheral blood and bone marrow following combination therapy using mass cytometry
 - To determine the impact of combination treatment on peripheral blood and bone marrow cells from patients treated in this manner on NY-ESO-1 target gene expression, NY-ESO-1 protein expression, NY-ESO-1 promoter methylation, and global DNA methylation.

8.3 Exploratory Endpoints

- To record the response rate (Complete Response (CR), Partial Response (PR) and Hematological Improvement (HI)) in MDS or low blast count AML patients treated with the combination in order to provide descriptive characteristics.
 - This will be assessed using results of blood counts on day 1 of each cycle.
 - A formal assessment of response will be performed Day 1 of Cycle 5 and every 4th cycle thereafter as long as patients remain on decitabine and at end of study including results of blood counts and a bone marrow biopsy. After 2 years on study, bone marrow assessments may be done every 6 cycles rather than every 4 cycles. Retrospective response assessment will include measurement of molecular measurable residual disease at serial time points.

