10.1.3 Decitabine

Decitabine will be given starting at dose level 1, which is the standard dose and schedule currently in use: 20 mg/m²/day for 5 consecutive days following standard of care guidelines (50).

Decitabine will be given at 20 mg/m²/day, intravenously, over 1 hour on days 1-5 followed by 23 days without decitabine at the discretion of the treating physician per their standard practice. Delays in dosing are allowed per standard institutional practice. Decitabine should be given Days 1-5 unless a delay is deemed necessary by the treating physician for patient safety. If required, dose de-escalation of decitabine to 15 mg/m² is provided for during the safety portion of the study.

Table 5 Dose Levels

Dose Level	CDX-1401/Poly-ICLC	Decitabine	Nivolumab
1	1mg/1.8mg	20mg/m ² days 1-5	3mg/kg days 1,15
-1	1mg/1.8mg	15mg/m ² days 1-5	3mg/kg days 1,15

There will be no dose modifications to the decitabine dose during the first 8 cycles of treatment. After cycle 8, dose reductions may be made at the discretion of the treating physician per their standard practice, but cycles should be given every 4 weeks unless a delay is deemed necessary by the treating physician for patient safety.

Delays in dosing up to 6 weeks are acceptable if deemed necessary for patient safety. Grade 4 neutropenia, transfusion dependence for platelets and red blood cells and the possibility of hospitalization for infections are expected toxicities of the underlying disease process and of standard treatment with decitabine.

Please see below for a detailed study calendar:

PROTOCOL TITLE: I 49217 - Phase 1 CDX-1401/ Poly-ICLC +Decitabine +Nivolumab in Patients with MDS or Low Blast Count AML

Treatment Plan: Cycle 1

Cycle 1														
Day	-14	1	2	3	4	5	6	7	8	...	15	...	28
CDX-1410	X											X		
Poly ICLC	X											X		
Decitabine (DAC)			X	X	X	X	X							
Nivolumab (NIVO)			X									X		

Treatment Plan: Cycles 2-4

Cycles 2-4														
Day	1	2	3	4	5	6	7	8	9	10	...	15	...	28
CDX-1410												X		
Poly ICLC												X		
Decitabine (DAC)	X	X	X	X	X									
Nivolumab (NIVO)	X											X		

PROTOCOL TITLE: I 49217 - Phase 1 CDX-1401/ Poly-ICLC +Decitabine +Nivolumab in Patients with MDS or Low Blast Count AML

Treatment Plan: Non-Vaccine Cycles:

Cycles 5-7, 9-11, 13-15, 17-19, 21-23, 25...														
Day	1	2	3	4	5	6	7	8	9	10	...	15	...	28
CDX-1410														
Poly ICLC														
Decitabine (DAC)	X	X	X	X	X									
Nivolumab (NIVO)	X													

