11.4 Evaluations Performed on Day 1 of each Cycle

The following evaluations will be performed prior to CDX-1401/poly ICLC dosing or infusion of decitabine on Day 1 of each cycle or prior to premedication, if administered (may be performed up to 3 days prior to day of infusion), unless otherwise indicated:

- Physical examination
- Vital signs (i.e., temperature, heart rate, respiratory rate, oxygen saturation, blood pressure, body weight)
- Hematology: CBC with manual differential (Once per week of each cycle during cycles 1-4, from cycles 5 onward on day 1 and as clinically indicated)
- Hematological Improvement (HI) in MDS or low blast count AML patients treated with the combination in order to provide descriptive characteristics.
 - This will be assessed using results of blood counts on day 1 of each cycle.
- Chemistry: CMP, LDH, uric acid, amylase and, lipase (Once per week each cycle during cycles 1-4, from cycles 5 onward on day 1 and as clinically indicated)
- ECOG performance status

PROTOCOL TITLE: I 49217 - Phase 1 CDX-1401/ Poly-ICLC +Decitabine +Nivolumab in Patients with MDS or Low Blast Count AML

- Correlative blood sampling prior to study drug dosing Once per week each cycle during Cycles 1-4; from Cycle 5 onward once every 2 weeks (see Section 11.11.1)
- Decitabine administration: Day 1-Day 5 of each cycle (per standard of care for patient safety)
- Nivolumab administration: Day 1 and Day 15 of each cycle (+/-7 days)
- Concomitant Medications
- Adverse events

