Appendix C ECOG Performance Status Scores

Description	Status
Fully active, able to carry on all pre-disease performance without restriction.	0
Restricted in physically strenuous activity but ambulatory and able to carry out work of a light or sedentary nature, e.g., light housework, office work.	1
Ambulatory and capable of all self-care but unable to carry out any work activities.	2
Capable of only limited self-care, confined to bed or chair more than 50% of waking hours.	3
Completely disabled. Cannot carry on any self-care. Totally confined to bed or chair.	4
Dead	5

PROTOCOL TITLE: I 49217 - Phase 1 CDX-1401/ Poly-ICLC +Decitabine +Nivolumab in Patients with MDS or Low Blast Count AML

Appendix D Response Criteria for MDS and AML According to Modified International Working Group Criteria

Response Criteria for MDS and AML patients according to modified IWG criteria	
Designation	Criteria for Response
Morphologic Leukemia Free state	<5% blasts in the marrow
Complete Response (CR)	Morphologic CR: BM blasts <5% with no dysplasia, in combination with CBC demonstrating: 1) platelets > 100K/mm ³ , 2) neutrophils > 1000/mm ³ Cytogenetic CR: As above + cytogenetics normal Molecular CR: As above + Molecular testing negative
Partial Remission (PR)	For MDS: BM blasts decreased by ≥50%, or less advanced MDS FAB classification than pretreatment. For AML: Blasts decreased by ≥50% or decrease to 5-25; Blasts ≤ 5% if Auer rod positive Platelets >100,000
Stable Disease (SD)	No PR, but no evidence of progression ≥ 2 months
Hematological Improvement (HI)	Erythroid Response (HI-E) 1) Major: Transfusion independence or 2g increase in Hg 2) Minor: 1 to 2g increase in Hg or 50% decrease in transfusion requirements Platelet Response (HI-P) 1) Major: absolute increase in platelets of 30K/mm ³ or development of transfusion independence 2) Minor 50% increase, net 10-30K/mm ³ Neutrophil Response (HI-N) 1) Major: 100% increase or absolute increase ≥500/mm ³ 2) Minor: 100% increase with value ≤500/mm ³

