- 2 Performed 30 days, 60 days, 90 days, and 180 days (± 3 days) following last dose of study drug (last immunization with CDX-1401/poly ICLC/nivolumab). Assessment may be collected via telephone if the patient elects to come off study and is no longer coming to clinic.
- 3 Height collected at baseline only.
- 4 Physical examination on day -14 and day 1 of each cycle (or up to 3 days prior to the beginning of a cycle) and at end of treatment
- 5 Vital signs including temperature, heart rate, oxygen saturation, respiratory rate, body weight and blood pressure prior to CDX-1401/poly ICLC dosing on day -14 and day 15 of each cycle (cycles 1-4) or day 1 of each 4th cycle (cycles 5+) and prior to decitabine dosing on day 1 of each cycle
- 6 CBC with manual differential

PROTOCOL TITLE: I 49217 - Phase 1 CDX-1401/ Poly-ICLC +Decitabine +Nivolumab in
Patients with MDS or Low Blast Count AML

- 7 Once per week each cycle during cycles 1-4, from cycles 5 onward on Day 1 and as clinically indicated. Used to assess hematologic improvement per modified International Working Group criteria for MDS on Day 1 every cycle 1.
- 8 CMP, LDH, uric acid, amylase and, lipase. Once per week each cycle during cycles 1-4 and, on Day 1 from cycle 5 and onward and, as clinically indicated.
- 9 Bone Marrow Aspirate and Biopsy, Flow Cytometry, Conventional Cytogenetics+/- FISH as appropriate. At the end of cycle 1 a Bone Marrow aspirate is to be done purely for collection of correlative specimens, unless the patient has demonstrated sufficient clinical response to warrant disease assessment at the discretion of the treating physician. **Note:** At the end of Cycle 1, if a bone marrow aspirate is not able to be done, a bone marrow biopsy may be performed instead. Thereafter a complete bone marrow assessment to be done every 4th cycle (per standard of care) for response assessment. If bone marrow is unable to be obtained due to dry tap, collected 4 additional green top tubes of peripheral blood.
- 10 **CDX-1401/poly-ICLC** administered on day -14 of cycle 1 and then *day 15 of every cycle for the first 4 cycles.*
NOTE: After Cycle 4: to be given on *day 1 of every 4th cycle as a booster (i.e. on day 1 of cycles 8, 12, 16, 20, 24).*
10a: Decitabine administered on days 1-5 of each cycle.
10b: Nivolumab administered every 2 weeks on days 1 and 15 of each cycle for the first 4 cycles.
Note: After Cycle 4: to be given on day 1 of every cycle 5 and above

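### Hematological improvement is read from day-1 counts with no confirmation, duration or transfusion-free condition, so a recently transfused or merely fluctuating patient can be scored as improved

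*Combined protocol and SAP*

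**What the plan says.** Section 8.3 makes HI part of the exploratory response rate, with CR and PR, and states: "This will be assessed using results of blood counts on day 1 of each cycle". Section 11.4 repeats this for HI specifically. Appendix J, footnote 7, says of the blood counts: "Used to assess hematologic improvement per modified International Working Group criteria for MDS on Day 1 every cycle 1" (the closing words look garbled, but the intent appears to be day 1 of each cycle).

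Appendix D sets the thresholds:
- Erythroid: "1) Major: Transfusion independence or 2g increase in Hg", and "Minor: 1 to 2g increase in Hg or 50% decrease in transfusion requirements".
- Platelets, major: a rise of 30K/mm³ "or development of transfusion independence".

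No HI line carries a duration, a repeat count or a transfusion-free interval. The only duration in that table, 2 months, belongs to stable disease.

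Section 10.1.3 lists "transfusion dependence for platelets and red blood cells" among the expected toxicities. Section 11.4 schedules hematology "Once per week of each cycle during cycles 1-4", then on day 1 and as clinically indicated.

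A separate formal response assessment, with counts and marrow, takes place on Cycle 5 Day 1 and every fourth cycle thereafter (sections 8.3 and 11.7). Section 16 says objective responses are graded at the end of every fourth cycle.

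**The concern.** The erythroid and platelet criteria join transfusion independence to the count rise with 'or'. Independence is an alternative route to HI and not a condition on the rise. A red-cell or platelet transfusion shortly before day 1 can therefore satisfy the criterion for that lineage, in a population expected to need transfusion.

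The second mechanism is repeated looking. Treatment has no fixed end (section 7), so on the per-cycle reading the number of day-1 counts compared with baseline is open-ended. A single excursion above the threshold is enough.

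The transfusion-based routes have a related gap: neither independence nor the 50% reduction has a reference period, so two assessors could score the same patient differently.

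At stake is whether the descriptive response rate can be interpreted. With at most 18 patients, each false HI moves a rate on all 18 by 1/18 = 5.6 percentage points.

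**Working it through.** **No plan figure to reproduce.** The documents give no rate, power or error figure for HI. The transfusion mechanism follows from the wording and cannot be quantified from the documents. Only fluctuation is quantified here.

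**Inputs from the documents.** Appendix D thresholds t: hemoglobin +1 g (minor or better), hemoglobin +2 g (major), platelets +30K (major).

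**Assumptions.**
- Within-patient SD σ: 0.3 to 1.0 g for hemoglobin, 10 to 20K for platelets.
- Independent Normal noise, one baseline count, no true change.
- K = 8 looks for the per-cycle reading. K = 2 for the every-fourth-cycle reading over the same 8 cycles.

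**Formulas.** Let B ~ N(0, σ²) be the baseline error and q(B) = 1 − Φ((t + B)/σ) the chance that a given later count qualifies.
- One look: 1 − Φ(t/(σ√2)). For t = 1 g and σ = 0.5 g: 1 − Φ(1.414) = 7.9%.
- Any of K looks: E[1 − (1 − q(B))^K].
- Two consecutive looks: the expectation over B of the chance of at least one adjacent qualifying pair; for K = 2 this is E[q(B)²].

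All looks share one baseline and so are correlated. At σ = 0.5 g, treating 8 looks as independent would give 1 − 0.9214⁸ = 48%; the shared baseline gives 31%.

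**Results: percent falsely meeting the threshold, any single look → two consecutive looks.**

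| Criterion | SD | 2 looks | 8 looks |
|---|---|---|---|
| Hg +1 g | 0.3 g | 1.7 → 0.1 | 5.3 → 0.6 |
| Hg +1 g | 0.5 g | 13 → 2.3 | 31 → 8.5 |
| Hg +1 g | 0.7 g | 25 → 6.1 | 49 → 19 |
| Hg +1 g | 1.0 g | 37 → 11 | 64 → 31 |
| Hg +2 g | 0.5 g | 0.4 → <0.1 | 1.5 → 0.1 |
| Hg +2 g | 0.7 g | 4.0 → 0.4 | 11 → 1.7 |
| Hg +2 g | 1.0 g | 13 → 2.3 | 31 → 8.5 |
| Plt +30K | 10K | 3.1 → 0.3 | 9.0 → 1.2 |
| Plt +30K | 15K | 13 → 2.3 | 31 → 8.5 |
| Plt +30K | 20K | 23 → 5.5 | 47 → 17 |

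At SD 0.3 g the +2 g criterion is essentially never met by chance. A simulation with 400,000 patients per scenario agrees with the 8-look hemoglobin figures.

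**In patients.** Suppose all 18 had no true change and 8 looks each. At SD 0.5 g, expected false Hg +1 g calls are 18 × 0.309 = 5.6 under any single look and 18 × 0.0845 = 1.5 under two consecutive looks.

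In every row the two-count rule removes more than half of the false calls. The smallest reduction is at SD 1.0 g with 8 looks, from 64% to 31%.

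**The case against.** The strongest reply is that the scoring rule is partly inferred. Section 8.3 names a data source and a day. It does not say that one count suffices or that an HI once met is permanent. The next item there sets a formal assessment at Cycle 5 and every fourth cycle, and section 16 grades objective responses on that timetable. This stands as an ambiguity, and it is why the 2-look column is shown. It does not remove the problem: nothing makes the formal assessment confirm an earlier HI, and that assessment also rests on counts at one time point.

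A second reply is that Appendix D summarizes cited Working Group criteria, which might carry a duration rule. That cannot be checked here. No such rule is printed in the protocol.

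Third, the endpoint is exploratory. Section 8.3 calls it descriptive, and section 19.3 rules out comparison with historical controls. This stands and sets the severity.

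A reader might infer that transfused patients *will* be counted as responders, or that the protocol ignores transfusion. Neither is supported. The text shows only that such patients *can* qualify, and Appendix D does use transfusion independence or reduction as routes to HI. Nor does the fault reach CR or PR, which also need marrow findings.

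**Conclusion.** The point holds as a gap in the HI definition. As written, a count rise on day 1 qualifies without confirmation, minimum duration or exclusion of recently transfused counts, and the transfusion-based criteria have no reference period.

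Under the assumptions above, false HI at the minor hemoglobin threshold could be anywhere from about 2% (2 looks, SD 0.3 g) to 64% (8 looks, SD 1.0 g). Major hemoglobin HI is much less exposed unless variability is large: about 1.5% at SD 0.5 g and 31% at SD 1.0 g with 8 looks. The SDs, number of looks and noise model are not in the documents, so these figures show what is possible and do not predict this trial's rate.

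Severity is minor. The DLT endpoint, dose decisions and secondary immune analyses do not depend on HI.

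**What to change.** In section 8.3 and Appendix D:
1. Count HI only when the threshold is met at two consecutive day-1 counts.
2. Do not score a count taken within a stated interval after transfusion of that lineage.
3. Give reference periods for transfusion independence and for the 50% reduction in requirements.
4. State whether the reported HI comes from the per-cycle assessment (section 8.3, section 11.4, Appendix J footnote 7) or from the every-fourth-cycle grading (section 16), and align the passages.

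No new blood draws are needed, because day-1 counts are already taken every cycle. One data item must be added: Appendix J has no transfusion line, and blood products are not named under concomitant medications. The other cost is a lower reported HI rate, including some true but brief improvements that would no longer count.

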9 DESIGN

This is an open-label, non-randomized Phase 1 study of CDX-1401 1 mg (intracutaneous) + poly-ICLC 1.8 mg (poly-ICLC will be given subcutaneously on each day of CDX-1401) vaccination, given in conjunction with decitabine x 5 days and nivolumab 3 mg/kg every 2 weeks. In dose level 1, Decitabine is dosed at 20 mg/m²/day for 5 days/28 day cycle (Day 1-Day 5 of each cycle).

9.1 Study Design

The primary objective of this Phase I study is to determine safety of the combinatorial regimen. The secondary objective is to assess immune and molecular epigenetic response. An exploratory

PROTOCOL TITLE: I 49217 - Phase 1 CDX-1401/ Poly-ICLC +Decitabine +Nivolumab in Patients with MDS or Low Blast Count AML

objective will be to record the response rate (including Complete Response (CR), Partial Response (PR) and Hematological Improvement (HI)) in the enrolled patients who will have a diagnosis of MDS or low blast count AML patients in order to provide descriptive characteristics.

This is a modified 3+3 design with a 12 patient expansion cohort at the maximum tolerated dose (MTD) or the maximum administered dose (MAD). We expect 18 patients to be enrolled (all at Dose Level +1), given experience with these treatments in other studies.

Three patients will be accrued at dose level 1. If 0 or 1 of the first 3 patients has a dose limiting toxicity (DLT, defined in section 10), then 3 more patients will be enrolled at the same dose. If a maximum of 1 of these six patients has a DLT, dose level 1 will be declared the maximum administered dose (MAD) and an additional 12 patients will be enrolled in an expansion cohort. Dose level +1 is considered the most likely MAD, given the low observed toxicity rates with NY-ESO-1 vaccine therapy. If the true DLT rate is 20%, there is an 85% probability of ending the trial with these 18 patients. Observed toxicity rates associated with NY-ESO-1 treatment have been below 20%. The accrual decision rules are shown in Table 4.

If either of the DLT thresholds at dose level 1 is exceeded, the same rules will be followed for dose level -1. If more than one third of patients at dose level -1 have a DLT, the study will be terminated.

Table 4 Dose De-Escalation Plan

Dose Level	Number of Subjects with a Dose-Limiting Toxicity at a Given Dose Level	Escalation Decision Rule
DL 1	2,3 out of 3	De-escalate to Dose -1. Enroll 3 patients
	0,1 out of 3	Maintain Dose Level 1. Enroll three more patients
	0,1 out of 6	Declare Dose Level 1 the maximum administered dose (MAD). Enroll expansion cohort of 12 additional patients.
	≥2 out of 6	De-escalate to Dose -1. Enroll 3 patients
DL -1	2,3 out of 3	Stop the study
	0,1 out of 3	Maintain Dose Level -1. Enroll three more patients
	0,1 out of 6	Declare Dose Level -1 the maximum tolerated dose (MTD). Enroll expansion cohort of 12 additional patients.
	≥2 out of 6	Stop the study.

Patients may elect to discontinue nivolumab and/or vaccine after Cycle 8 and remain on study receiving single agent decitabine to allow collection of the secondary and exploratory endpoints as described above.

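### The 85% chance of completing at Dose Level 1 (Section 9.1, 20% DLT rate) does not follow from the stated rule, which gives 65.5%; the threshold should be confirmed and the figure corrected

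*Combined protocol and SAP*

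**What the plan says.** Section 9.1 describes a modified 3+3 with de-escalation only.

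- **First step at Dose Level 1.** "If 0 or 1 of the first 3 patients has a dose limiting toxicity", three more patients are treated at that dose.
- **Second step at Dose Level 1.** "If a maximum of 1 of these six patients has a DLT, dose level 1 will be declared the maximum administered dose (MAD"). Table 4 agrees: 0 or 1 DLT in 6 leads to "Declare Dose Level 1 the maximum administered dose (MAD). Enroll expansion cohort of 12 additional patients", and 2 or more in 6 leads to Dose Level -1.
- **Expected size.** "We expect 18 patients to be enrolled (all at Dose Level +1), given experience with these treatments in other studies". That is 6 + 12 = 18.
- **Operating characteristic.** "If the true DLT rate is 20%, there is an 85% probability of ending the trial with these 18 patients".
- **Dose Level -1.** The text applies the same rules as at Dose Level 1 and then adds: "If more than one third of patients at dose level -1 have a DLT, the study will be terminated". Table 4's entry for 2 or more of 6 at that level is "Stop the study".

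**The concern.** The 85% stands beside the rule it is meant to describe, and it looks too high for a rule that fails at 2 DLTs in 6 when the true rate is 20%.

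It is the only operating characteristic given for the dose-finding part; the calculation in Section 19.1 concerns the 12-patient expansion cohort. A reader weighing the expectation that all 18 patients will be treated at Dose Level 1 takes from it that a 20% DLT rate carries about a 1 in 7 chance of not finishing there.

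The mismatch also raises doubt about which threshold was meant. The Dose Level -1 sentence stops the study only when the DLT proportion exceeds one third. Two of 6 is exactly one third, so that sentence does not trigger a stop where Table 4 does.

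**Working it through.** **Inputs** (all from Section 9.1 and Table 4): true DLT rate p = 0.20; two groups of 3 patients; continue after the first group if at most 1 has a DLT; open the expansion if at most 1 of the 6 has a DLT; stated probability 85%.

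**Probabilities for one group of 3 at p = 0.20**

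- P(0 DLTs) = 0.8^3 = 0.512
- P(1) = 3(0.2)(0.8^2) = 0.384
- P(2) = 3(0.2^2)(0.8) = 0.096
- P(3) = 0.2^3 = 0.008
- Hence P(at most 1) = 0.896 and P(at most 2) = 0.992.

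**Attempt to reproduce 85% from the stated rule**

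P(0 in first 3) × P(at most 1 in next 3) + P(1 in first 3) × P(0 in next 3)
= 0.512 × 0.896 + 0.384 × 0.512
= 0.458752 + 0.196608 = **0.65536**

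The single-step binomial gives the same answer: 0.8^6 + 6(0.2)(0.8^5) = 0.262144 + 0.393216 = 0.65536. The first step does not alter the result, because at most 1 of 6 implies at most 1 of the first 3.

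**Where the remaining 34.5% goes**

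- Leaves after the first 3: 0.096 + 0.008 = 0.104
- Leaves after 6: 0.896 − 0.65536 = 0.24064
- Total: 0.34464

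**Other readings at p = 0.20**

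| Reading | Probability |
|---|---|
| Stated rule: ≤1 of 3, then ≤1 of 6 | 65.5% |
| First step only: ≤1 of 3 | 89.6% |
| ≤1 in each group of 3 | 80.3% |
| Conventional 3+3 (0 of 3, or 1 of 3 then 0 of 3) | 70.9% |
| ≤2 of 6 with no first step | 90.1% |
| Stated rule passed at either dose level, p = 0.20 at both | 88.1% |
| Stated rule and ≤4 of 12 in the expansion | 60.8% |
| **≤1 of 3, then ≤2 of 6** | **85.2%** |

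The last line is 0.512 × 0.992 + 0.384 × 0.896 = 0.507904 + 0.344064 = 0.851968.

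That rule differs from the stated one only when exactly 2 of 6 have a DLT after at most 1 in the first 3: 0.512 × 0.096 + 0.384 × 0.384 = 0.049152 + 0.147456 = 0.196608. This is the whole gap between 0.851968 and 0.65536.

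**The two rules at other DLT rates**

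| True DLT rate | ≤1 of 6 (stated) | ≤1 of 3, then ≤2 of 6 |
|---|---|---|
| 10% | 88.6% | 96.4% |
| 15% | 77.6% | 91.7% |
| 20% | 65.5% | 85.2% |
| 27% | 48.7% | 73.6% |

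Under the stated rule, 85% would require a true DLT rate of about 11.7%.

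**The case against.** The strongest reply is that the 85% is a descriptive remark. No accrual, de-escalation, stopping or analysis rule uses it, and Section 19 does not cite it. The Dose Level 1 rule is the same in the text and in Table 4, so a site would act identically whether the sentence said 85% or 66%. Completion at Dose Level 1 also remains the most likely outcome at 20%, and it reaches 88.6% if the true rate is 10%. All of this stands. It limits the consequences but does not make the figure right.

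A second reply is that the Dose Level -1 sentence and Table 4 can both be obeyed. The sentence says when to stop and is silent at exactly one third, while Table 4, and the statement that the same rules apply, point to stopping. That is a fair reading, and it makes stopping the better-supported action. Two different limits are still written for one safety decision, and at 2 of 6 they do not coincide.

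A third reply is that the at-most-1-of-6 limit appears consistently, so the number is probably what is wrong. That is reasonable. The match with the looser rule was found by trying alternatives and does not prove where the 85% came from. It is still reason enough to ask before editing.

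Reading the figure as success at either dose level does not rescue it. That gives 88.1%, and a trial completed after de-escalation would treat 3 + 6 + 12 = 21 or 6 + 6 + 12 = 24 patients, not these 18.

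**Conclusion.** The stated operating characteristic is wrong for the rule as written. At a 20% DLT rate the probability of completing the 18-patient path at Dose Level 1 is 65.5%, about 20 percentage points below the 85% claimed, and the chance of leaving that path is more than twice what is implied (34.5% against 15%). The result is exact given the written rule and assumes only independent patients with a common DLT rate.

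That the 85% came from a 2-of-6 tolerance is an inference. That it does not come from the 1-of-6 rule is not. Separately, the Dose Level -1 sentence does not set the same threshold as Table 4 and needs correcting whatever the origin of the 85%.

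**What to change.** First confirm that at most 1 of 6 is the intended limit.

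- **If it is:** replace 85% with 66% in Section 9.1, and reword the Dose Level -1 sentence so that the study stops at 2 or more DLTs in 6, as in Table 4. The cost is two wording corrections and a less favourable stated figure. The Dose Level 1 rule does not change.
- **If 2 of 6 was meant to be tolerated:** keep 85%, and correct the Section 9.1 rule and Table 4. This is a change to the de-escalation and stopping rule itself, and a dose could then be accepted with an observed DLT rate of one third.
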